**Table 3Karch and Lasagna algorithm modified by Naranjo**

Thus, the degree of certainty required to establish the PI as the causal agent of the harmful phenomenon occurring to the subject of the clinical study is determined. This can also be indicated directly by the PI based on their clinical experience or through the voluntary application of the aforementioned tool. However , it is important that the researcher and the UFTLS consider the following arguments in favor of a causal relationship:

- a) Strength of association, which refers to the number of cases in relation to those exposed.
- b) The consistency of the data, that is, the presence of a common characteristic or pattern.
- c) The exposure-effect pattern, which determines the relationship with the site of onset, time, dose and reversibility after suppression.

- d) Biological plausibility, which refers to the possible pharmacological or pathophysiological mechanisms involved in the development or presentation of the adverse event.
- e) Experimental findings, for example, the appearance of anomalous metabolites or high levels of drug or its biotransformation product.
- f) Analogy, which refers to the experience acquired with other related drugs, adverse reactions frequently produced by the same family of pharmacological agents.
- g) Nature and characteristics of the data, i.e. objectivity, accuracy and validity of the relevant documentation. [47]

## 8.5 Unanticipated problems

Unanticipated problems (ANP) are considered situations that pose risks to the participating subjects, generally any incident, experience or result that meets all of the following criteria:

- Unexpected in terms of its nature, severity, or frequency in relation to: 1) study-related documents such as the investigator's manual, study protocol, and informed consent form; and 2) the characteristics of the study population.
- Related or possibly related to your participation in the study (possibly related means that there is a reasonable possibility that the incident or results were caused by study procedures).
- Indication that the research places participants at greater risk of harm (including physical, psychological, economic, or social) than previously recognized.

### 8.5.1 PNAs Report

The PI will be responsible for reporting PNAs to the sponsor, the IC, and the IEC. The report should contain the following information:

- Study identification: protocol title and number, name of the PI and, where applicable, the center.
- Detailed description of the event, incident, experience or outcome.
- Explanation, justification of the reasons why the incident represents a PNA.
- Description of changes to the protocol or corrective actions taken or proposed in response to the NAP.

PNAs that are EAS must be reported to the IEC and the sponsor within the first 24 hours of the IP becoming aware of them.

Any other PNA will be reported to the IEC and the sponsor within the first 5 business days after the IP becomes aware of it.

## 9. Study monitoring

---

The study sponsor is responsible for monitoring the study. Monitoring activities include, but are not limited to: general safety monitoring, general study quality monitoring, study site monitoring, adverse event detection monitoring, reporting and follow-up, monitoring to resolve data entry discrepancies, etc.

Responsibility for monitoring activities and ultimate responsibility for monitoring rests with the sponsor.

The details of the monitoring activities are specified in a separate document from this protocol in a Monitoring Plan.

### 9.1 Monitoring of study centers

The research centers participating in the study will be monitored. At least one initial visit and one closing visit must be conducted for each center, although one or more follow-up visits may be required between these two mandatory visits.

The initial visit must be conducted before the first participant is enrolled at that center. During this visit, the monitor will verify that the materials to be used during the study have been received and that the personnel involved in study activities have been trained in the study. The monitor will also verify compliance with applicable regulatory requirements and standard operating procedures.

At the follow-up visit(s), the monitor will review the study documents to confirm that the research protocol and applicable standard operating procedures are being followed, that data entry is complete and timely, and that adverse event reporting is being conducted appropriately. At each visit, the monitor will discuss the findings with the investigator, and the investigator will determine the appropriate actions to be taken.

The closing visit will take place at the end of the study, once the last participant at the site has been discharged from follow-up. During this visit, the monitor will verify that the site has all the necessary documentation for archiving, that all biological samples have been sent for analysis, that all study drug (used and unused) has been recovered and sent to the sponsor, and that all unused materials have been retrieved.

Details of monitoring are set out in the relevant plan.

### 9.2 Audit and quality control

To ensure compliance with GCPs and all applicable regulatory requirements, Laboratorios Sophia, SA de CV may conduct quality assurance audits. Regulatory agencies may also conduct a regulatory inspection of this study.

Details of the audit process are set out separately in an Audit Plan.

### 9.2.1 Pre-study audit

The study centers included in the study will be subject to a feasibility visit prior to center selection, where they will be verified to meet the minimum requirements indicated by the sponsor.

### 9.2.2 Audit during the conduct of the study

They may take place at any time before, during, or after the conclusion of the study. If an audit or inspection is conducted, the investigator and the institution must agree to allow the auditor/inspector direct access to all relevant documents and must allocate their time and staff time to the auditor/inspector to discuss the findings and any pertinent issues. If the audit has not been scheduled by the sponsor, the center must notify Laboratorios Sophia, SA de CV immediately.

# 10. Statistical analysis

---

## 10.1 Data analysis

### 10.1.1 Statistical analysis

Statistical analysis will be performed by staff of Laboratorios Sophia, SA de CV. The statistical program SPSS version 19.0 (IBM Corporation, Armonk, NY, USA) will be used.

The designated personnel will be blinded to the intervention groups. Coding will be performed using consecutive numbers for each intervention group.

The data will be collected and organized in an Excel spreadsheet (Microsoft® Office). The data will then be exported to the SPSS software platform. The variables will be categorized according to their nature (see Table 2).

### 10.1.2 Data interpretation

The Kolmogorov-Smirnov and Shapiro-Wilk tests will be performed, as applicable, to determine whether the distribution is normal in the results obtained in each study group.

The results of continuous quantitative variables will be presented in measures of central tendency: mean, standard deviation and ranges.

The statistical analysis of continuous quantitative variables to find significant differences (  $p<0.05$  ) will be as follows:

- Intra-group analysis: will be determined using the Wilcoxon rank test for quantitative variables.
- Between-group analysis: Differences between groups will be analyzed using the Student t-test or the Mann-Whitney U statistic if applicable ( it will be used to test whether a group of data comes from the same population).

The level of difference considered significant will be an alpha ( $\alpha$ ) of 0.05 or less. A 95% CI will be considered for noninferiority criteria.

The results of the nominal and ordinal qualitative variables will be presented in frequencies, proportions and percentages.

Statistical analysis to identify significant differences in qualitative variables will be performed by creating 2x2 contingency tables and will be carried out as follows:

- Intra-group difference: McNemar's test. This test is applied to 2x2 contingency tables with a dichotomous trait, with matched pairs of subjects, to determine whether the marginal frequencies of the row and column are equal (marginal homogeneity).

- Difference between groups: Pearson's Chi-square test (  $X^2$  ) or Fisher's exact test for expected values less than 5.

The level of difference to consider significance will be an alpha ( $\alpha$ ) of 0.05 or less.

For adverse event reporting, all eyes of participants randomized to an intervention group after the baseline visit will be considered. Results will be expressed as the number of subjects.

The final results report will be displayed in tables or graphs, as appropriate.

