### 3.4.2 Efficacy hypothesis

$H_0$  = Nanodrop® is inferior to Systane® Balance by more than 5 points on the OSDI test score

$$H_0: \mu_A - \mu_B > \delta$$

$H_1$  = Nanodrop® is inferior to Systane® Balance by 5 points or less on the OSDI test score

$$H_1: \mu_A - \mu_B \leq \delta$$

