## 7.4 Outcome variables

### 7.4.1 Primary outcome variables

- OSDI Test Score (TE: Day 29)
- Incidence of unexpected AEs related to the PI (TE: day 8 and 29)

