## 7.4.4 Definition of variables, methods and scales to be used for measurement

Variable	Guy	Unit (symbol)	Measurement method	Normal value	Evaluation time	Statistical test
Primary outcome						
OSDI	Discreet	Points (-)	Questionnaire	< 13	VB and VF	Mann-Whitney U
Unexpected EAs related to PI	Discreet	Number of cases (n)	Counting	0	VB, V1 and VF	Mann-Whitney U
Unexpected AEs related to the PI (bis)	Nominal categorical	Present/absent (-)	Observation	Absent	VB, V1 and VF	$\chi^2$ or Fisher's exact test
Of secondary outcome						
MAVC	Discreet	Fraction (-)	Snellen chart	1	VB, V1 and VF	Mann-Whitney U
TRPL with fluorescein	Continue	Seconds (s)	Direct observation with slit lamp and blue filter	>10s	VB, V1 and VF	Mann-Whitney U
Corneal staining with fluorescein	Ordinal	Degrees (-)	Direct observation with a slit lamp on the Oxford scale	0	VB, V1 and VF	$\chi^2$ or Fisher's exact test
Conjunctival staining with lissamine green	Ordinal	Degrees (-)	Direct observation with slit lamp and cobalt blue filter, Oxford scale graduation	0	VB, V1 and VF	$\chi^2$ or Fisher's exact test
EA	Discreet	Number of cases (n)	Counting	0	VB, V1 and VF	Mann-Whitney U
EA (repeat)	Nominal categorical	Present/absent (-)	Observation	Absent	VB, V1 and VF	$\chi^2$ or Fisher's exact
Exploratory						
Number of applications made daily	Discreet	Number of applications (n)	Count by Subject's Diary	>4	V1 and VF	Mann-Whitney U

**Table 2**Operational definition of variables

The variables, method, and scales for their measurement are described in detail below. They are listed in order according to **Table 2**

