5.0 Sample Size Calculation

For the sample size calculation, changes in the OSDI (*Ocular Surface Dehydration Index*) questionnaire score were considered, in studies with ocular lubricants in patients with dry eye disease (DED), as the primary efficacy variable.

PRO-176 (Nanodrop®; Laboratorios Sophia, SA de CV) is expected to be non-inferior to its comparator (Systane® Balance; Alcon Research Ltd, Fort Worth, TX, USA), according to the following working hypotheses:

$$H_0: \varepsilon \leq \delta$$

$$H_1: \varepsilon > \delta$$

Where $\mu_A - \mu_B = \varepsilon$, is the true difference in means between the test treatment (PRO-176) and the active control (Systane® Balance). Where δ is the non-inferiority margin, and the ratio of the sample sizes between the two groups is given by:

$$k = \frac{n_A}{n_B}$$

Calculations were performed using the non-inferiority equation for two means and for statistical power (Chow et al., 2008).

$$n_A = kn_B \text{ y } n_B = \left(1 + \frac{1}{k}\right) \left(\sigma \frac{z_{1-\alpha} + z_{1-\beta}}{\mu_A - \mu_B - \delta} \right)^2$$

$$1 - \beta = \theta(z - z_{1-\alpha}) + \theta(-z - z_{1-\alpha}) , \quad z = \frac{\pi_A - \pi_B - \delta}{\sigma \sqrt{\frac{1}{n_A} + \frac{1}{n_B}}}$$

Where σ is the standard deviation, $k=nA/nB$ is the agreement ratio, θ is the standard Normal distribution function, α is the type I error (confidence interval), β is the type II error (meaning that $1-\beta$ corresponds to the power) and δ is the test margin.

With a power of 80% ($\beta=0.20$), a significance level of 0.05 (α) and a non-inferiority margin (δ) of -5 points on the OSDI score (Grubbs et al., 2014; Labetoulle et al., 2017; Pérez-Balbuena et al, 2016).

The calculation was based on the study by Benitez-Del-Castillo et al., 2016. Phase I and II clinical study. A total of 156 healthy subjects and patients with DED were enrolled. The Phase I study included 30 healthy volunteers; it was a single-center, parallel-group, open-label study. Phase II was a multicenter, double-blind study. In Phase I, SYL1001 was administered at 1.125% and 2.25% doses, and in Phase II, at 0.375% and 0.75%. After 10 days of treatment, the primary efficacy variable was the effect on the OSDI score. OSDI scores were significantly reduced compared to baseline ($p<0.01$) for all treatments in both Phase I and Phase II. No statistical differences were observed between treatments.

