6.0 Analysis Plan

The variables to be considered in the protocol are described below.

Primary efficacy outcome variables:

- OSDI test score.

Secondary efficacy outcome variables:

- Changes in best corrected visual acuity (BCVA).
- Changes in corneal and conjunctival staining with lissamine green.
- Corneal and conjunctival staining changes with fluorescein.
- Changes in tear film break-up time (TRL) with fluorescein.

Security Variables

Primary Safety outcome variable:

- Incidence of unexpected adverse events (AEs) related to the drug.

Secondary safety outcome variable:

- Incidence of expected AEs.

Table 2. Operational Definition of the Variables

Variable	Definition Conceptual	Definition Operational	Scale of measurement	Category
Events adverse	Any event adverse adverse doctor that occurs in a patient or clinical research subject who was administered a collected through the pharmaceutical product and that, not necessarily has a relationship causal with this treatment.	The events adverse effects manifested during the conduct of the study will be electronic CRF.	• Nominal • Frequency: • Intensity: 0= Mild 1= Moderate 2= Severe • Causality: 0=Probably or possibly related. 1=Unlikely related.	Subjects presenting AE/Total number of exposed subjects.
Ocular Surface Disease Index Score (OSDI).	The OSDI is a questionnaire designed to establish a severity and classification of the dry eye according to its symptoms.	The evaluator will apply the questionnaire to the subject and allow him to do so answer in calm without any kind of pressure and/or coercion. See Annex 1. OSDI.	Continue	Score: $OSDI = \frac{(Suma\ del\ puntaje)25}{\# \ de \ respuestas \ contestadas}$
Changes in corrected visual acuity (BCVA).	Visual acuity corrected (BCVA) is a test of visual function. Spatial VA is the ability to distinguish separate elements of an object and identify them as a whole. It is	Booklet of Snellen	Quantitative discrete.	Fraction, normal value = 0.6 to 2.0

It quantifies the minimum angle of separation (located at the nodal point of the eye) between two objects that allows them to be perceived as separate objects.
				

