The statistical analysis of continuous **quantitative variables** to find significant differences (p) will be as follows:

- Intra-group analysis: will be determined using the Wilcoxon rank test, for quantitative variables (Woolson, 2008).
- Between-group analysis: differences between groups will be analyzed using the Student t-test or the Mann-Whitney U statistic if applicable (it will be used to test whether a group of data comes from the same population).

The level of difference to consider significance will be an alpha (α) of 0.05 or less. It will be considered a 95% CI for non-inferiority criteria (Schumi & Wittes, 2011; Easty et al., 2006).

The result of the nominal and ordinal qualitative variables will be presented in frequencies, proportions and percentages, see table 2.

Statistical analysis to identify significant differences in **qualitative variables** will be performed by creating 2x2 contingency tables and will be carried out as follows:

- Intra-group difference: McNemar's test (Klingenberg & Agresti, 2006). This test is applied to 2x2 contingency tables with a dichotomous trait, with matched subject pairs, to determine whether the marginal frequencies of the row and column are equal (marginal homogeneity).
- Difference between groups: Chi-square test (χ^2) Pearson's or Fisher's exact test in values expected under 5.

The level of difference to consider significance will be an alpha (α) of 0.05 or less.

For the reporting of adverse events, all eyes of participants who were randomized to an intervention group after the baseline visit will be considered.

The final results report will be displayed in tables or graphs, as appropriate.

Subjects who meet a minimum adherence of 70% will be included in the statistical analysis to meet the study objective, based on the weight of the PI. In cases where the container is not returned or has not been physically intact, adherence will be measured using the subject's diary.

The investigational drug will be considered safe and effective when there are no clinical and statistical differences in all primary outcome variables, with respect to its comparator.
(Systaine® Balance).

Table 3. Triangulation of concepts

Variable Type	Variable	A1	B1	B2	C1	C2	D1	E1	E2	E3
Background										
A1	Demographics						DT			
Basal										
B1	Medical record				DT					
B2	Comprehensive ophthalmological evaluation				DT		TB	TB		TB
Security										
C1	Unexpected/related AEs				TB		TB		TB	TB
C2	EAs				TB		TB		TB	TB

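### The SAP declares success for OSDI when no difference is found, which conflicts with the 5-point non-inferiority criterion; the interval, hypothesis direction and margin sign are also not settled

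*Protocol*

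**What the plan says.** **Target.** Protocol 7.4.1 lists "OSDI Test Score (TE: Day 29") as the primary efficacy variable. Protocol 3.4.2 states the null as "Nanodrop® is inferior to Systane® Balance by more than 5 points on the OSDI test score", in symbols a difference in means greater than delta. Protocol 10.2.2 defines that difference as test minus active control.

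**Between-group test.** Protocol 10.1.2 reads "Differences between groups will be analyzed using the Student t-test or the Mann-Whitney U statistic if applicable"; the Protocol synopsis and SAP 7.0 say much the same, with normality tests run beforehand. Table 2 in Protocol 7.4.4 names one test only: "OSDI Discreet Points (-) Questionnaire < 13 VB and VF Mann-Whitney U". SAP Table 2 classes the score as continuous ("See Annex 1. OSDI. Continue").

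**Non-inferiority criterion.** Protocol 10.1.2: "A 95% CI will be considered for noninferiority criteria". SAP 7.0 repeats this. Neither gives the sidedness, the method of construction or the limit to be compared with the margin.

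**Success statement.** SAP 7.0: "The investigational drug will be considered safe and effective when there are no clinical and statistical differences in all primary outcome variables" relative to the comparator. The meaning of clinical is not defined.

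**Margin and direction.** Protocol 3.4.2 uses 5 points. Protocol 10.2.2 keeps the same direction, labels both hypotheses H0, and sets delta at -5. SAP 5.0 reverses the inequality and also has "a non-inferiority margin (δ) of -5 points on the OSDI score".

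**Baseline.** OSDI is measured at the baseline and final visits (Protocol 1.3, 7.4.4, 7.5.1.1, 7.5.1.3). No between-group analysis uses the baseline value, and SAP Table 3 codes OSDI as descriptive and bivariate only.

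**The concern.** Failing to find a difference is not evidence of non-inferiority. A rule built on it becomes easier to satisfy as the trial becomes noisier, whereas a non-inferiority interval becomes harder to satisfy. With both in the same SAP section, one dataset can be declared a success under one sentence and a failure under another, so the primary conclusion is not fixed before the data are seen.

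The remaining gaps make the interval hard to apply even if it is meant to govern. The analyst must choose the sidedness and the limit. The test that Protocol Table 2 names for OSDI does not estimate the difference in means in the hypothesis. The printed hypotheses point different ways depending on the section. A smaller point is that a baseline measurement which could narrow the interval goes unused between groups.

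**Working it through.** **Inputs.** Margin 5 points (Protocol 3.4.2). SD 17.1 (Protocol 10.2.2; SAP 5.0 prints the same number as δ), assumed to be the SD of the final score. Evaluable subjects 51 per arm (Protocol 10.1.4, SAP 5.0). OSDI is higher when worse, and d is the true difference, Nanodrop minus Systane Balance.

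The plan gives no pass probability for either rule, so there is none to reproduce. Its nearest figure, 51 per arm, does not follow from the printed formula: 2 × [17.1 × (1.645 + 0.842) / distance]² gives 98, 145 or 238 per arm for distances to the margin of 6.1, 5 and 3.9. That is a separate sample-size matter; 51 is used here only as the planned evaluable number.

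**Interval width.** SE = 17.1 × √(2/51) = 3.386. The two-sided 95% half-width is 1.984 × 3.386 = 6.72.

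- Observed difference 0: interval -6.72 to 6.72. No significant difference, so the statistical half of the SAP rule is met; the upper limit exceeds 5, so non-inferiority fails.
- Observed difference -7 (Nanodrop better): interval -13.72 to -0.28. Non-inferiority passes; the SAP rule, read literally, fails.
- An upper limit below 5 needs an observed difference below 5 - 6.72 = -1.72. With a one-sided 95% bound (1.660 × 3.386 = 5.62) it needs one below -0.62. The unstated sidedness therefore matters.

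**Pass probabilities, OSDI part only, 51 per arm.** No significant difference: P(|T| < 1.984), T noncentral t on 100 df with noncentrality d/3.386. Interval rule: P(T < -1.984), noncentrality (d - 5)/3.386.

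| True d | No significant difference | Also observed difference under 5 in size | Two-sided 95% upper limit below 5 |
|---|---|---|---|
| 0 | 95% | 86% | 31% |
| 5 | 69% | 50% | 2.5% |
| 8 | 35% | 19% | 0.2% |

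The third column is one assumed reading of clinical. At d = 5 the first and last rules disagree in 67% of simulated trials. With 63 per arm (SE 3.047) the 69% becomes 63%.

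**Other reading of 17.1.** If it is the SD of change, with equal SDs at both visits, the score SD is 17.1/√(2(1 - ρ)) = 14.45, 17.10 or 22.08 for an assumed baseline-to-final correlation ρ of 0.3, 0.5 or 0.7. The 69% then becomes 59%, 69% or 79%.

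**Direction and sign**

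| Section | Statement | On the score (higher is worse) | On the reduction (higher is better) |
|---|---|---|---|
| Protocol 3.4.2 | H1: difference ≤ δ, 5 points | Nanodrop at most 5 worse: coherent | Does not limit inferiority |
| Protocol 10.2.2 | second hypothesis: ε ≤ δ, δ = -5 | Nanodrop at least 5 better | Nanodrop at least 5 worse |
| SAP 5.0 | H1: ε > δ, δ = -5 | Does not limit inferiority | Nanodrop less than 5 worse: coherent |

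The Protocol hypothesis works on the score and the SAP hypothesis works on the reduction. Protocol 10.2.2 works on neither.

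**Baseline adjustment.** The adjusted SD is 17.1 × √(1 - ρ²), and ρ is not in the documents. The half-width is 1.984 × adjusted SD × √(2/51) × √(1 + 1/98). Power with equal treatments is Φ(5/[adjusted SD × √(2/51)] - z).

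| Assumed ρ | Adjusted SD | Half-width | Power, one-sided 2.5% | Power, one-sided 5% |
|---|---|---|---|---|
| unadjusted | 17.10 | 6.7 | 31% | 43% |
| 0.3 | 16.31 | 6.4 | 34% | 46% |
| 0.5 | 14.81 | 5.8 | 40% | 52% |
| 0.7 | 12.21 | 4.8 | 54% | 66% |

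If 17.1 is instead the SD of change, power at one-sided 2.5% goes from 42%, 31% and 21% unadjusted to 45%, 40% and 36% adjusted.

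**The case against.** The strongest reply is that the plan's intent is clear. The objective is non-inferiority, SAP 7.0 itself names a 95% interval for it, and if clinical means the 5-point margin judged by that interval, the closing sentence is no laxer than the interval rule. The text is evidently a translation, so that sentence may be a loose summary. This stands in part: the 69% leaves out the word clinical altogether, and the 50% figure is nearly automatic, since about half of observed differences fall below a true value of 5. But the SAP does not define the word, and even on the benign reading the sentence still demands no statistical difference, which a non-inferiority claim does not require.

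A reader might infer several stronger things that the documents do not support:

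- That the target is undefined. Protocol 3.4.2, 7.4.1 and 10.2.2 together give a difference in means, in OSDI points, on the day-29 score. What is missing is how the interval is built and read.
- That a Mann-Whitney p-value is to be compared with 5 points. No section says so. The tests are described as looking for significant differences, and the interval is stated separately. The odd entry is Protocol Table 2, which names only the rank test.
- That an unadjusted comparison is invalid. Under randomisation it is valid, and leaving out baseline is a design choice that costs precision.
- That 17.1 is certainly the SD of the score. It is introduced beside reductions of 17.6 and 16.5, which points towards change; the documents do not say.

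**Conclusion.** The SAP's success sentence is not a non-inferiority rule, and it conflicts with the interval criterion and the 5-point hypothesis. For a product exactly at the margin, the chance of meeting it on OSDI is 69% on its statistical half, or about 50% on one reading of clinical, against 2.5% under a two-sided 95% interval. These figures rest on 51 per arm and on 17.1 as the SD of the final score; under the SD-of-change reading the 69% ranges from 59% to 79% for the correlations tried. They concern OSDI alone; the sentence also covers the primary safety variable.

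The interval's sidedness, construction and decisive limit are unstated, and the hypotheses and margin sign contradict one another across Protocol 3.4.2, Protocol 10.2.2 and SAP 5.0. These should be corrected before unblinding.

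Baseline adjustment is a recommendation, not the correction of an error. Its gain depends on an undocumented correlation, which the entry threshold of OSDI 13 or more may lower. With equal treatments it does not by itself restore 80% power at any value tried.

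**What to change.** 1. Replace the SAP 7.0 success sentence, for OSDI, with one rule: mean difference in final-visit OSDI score, Nanodrop minus Systane Balance, higher being worse; two-sided 95% confidence interval; non-inferior if the upper limit is below 5 points.
2. Align the hypotheses and margin sign in Protocol 3.4.2, Protocol 10.2.2 and SAP 5.0 with that rule.
3. Align the variable type and test for OSDI in the Protocol synopsis, Protocol 7.4.4 and 10.1.2, and SAP 6.0 and 7.0. Drop the normality-based switch for this endpoint and keep the rank test as a sensitivity analysis.
4. Reconcile the final visit: the Protocol schedule has day 29, while SAP Table 1 has day 31 and no OSDI row.
5. State whether 17.1 is the SD of the score or of change. Adjustment does not answer that.
6. Recommended: estimate the difference by ANCOVA of final OSDI on treatment and baseline OSDI, which gives the same treatment effect for score or change.

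The cost is Protocol and SAP wording. ANCOVA uses one further degree of freedom, a loss in standard error of about 0.5% at worst with 51 per arm (√(1 + 1/98) = 1.005). No new data or visits are needed.
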